8.3. Subject Withdrawal Criteria

8.3.1. Early Discontinuation of Study Drug

Subjects may voluntarily withdraw from the study at any time and for any reason without prejudice to further treatment. A subject must permanently discontinue study drug under any of the following circumstances:

- The subject becomes pregnant. Study drug must be discontinued immediately and the pregnancy reported to the Sponsor.
- The subject wishes to discontinue study drug treatment for any reason.
- The subject experiences a medical emergency that necessitates discontinuing study drug treatment.
- The Investigator, Sponsor, or subject's primary care physician decides to discontinue treatment for medical reasons or due to the subject's noncompliance with the protocol.
- For Cohort 1 subjects, the subject experiences deterioration of renal function during corticosteroid tapering period, as determined by the Investigator.

The reason for termination of study drug before study completion must be recorded in the subject's case report form (CRF). The subject should complete all scheduled study visits provided written consent to do so has not been withdrawn.

8.3.2. Subject Withdrawal from the Study

A subject must be withdrawn from the study and discontinue study drug under the following circumstances:

- The subject withdraws consent to participate in the study.
- The Investigator or subject's primary care physician decides that the subject should be withdrawn from the study.
- The Sponsor decides that the subject should be withdrawn or the Sponsor discontinues the study for any reason.

The reason for withdrawal must be recorded in the subject's CRF. The subject should complete the evaluations scheduled for the Follow-Up Visit 1, provided written consent to do so has not been withdrawn. Subjects who are withdrawn may be replaced at the discretion of the Sponsor in consultation with the Investigator in order to meet study objectives.

8.3.3. Notification of Withdrawal

When a study participant is withdrawn from the study protocol, voluntarily or involuntarily, the Investigator will notify the Sponsor and the IRB/IEC as required, and provide the reasons for subject withdrawal.

9. STUDY DRUG

9.1. OMS721

OMS721 is manufactured under current Good Manufacturing Practices (cGMP) for investigational use. OMS721 is a human IgG4 mAb directed against MASP-2.

9.1.1. Packaging and Labeling

[REDACTED]

[REDACTED]

[REDACTED]

[REDACTED]

[REDACTED]

[REDACTED]

[REDACTED]

9.1.2. Blinding

Cohort 1

No blinding is necessary for Cohort 1 since all subjects receive OMS721.

Cohort 2 and Cohort 3

Subjects in Cohort 2 and Cohort 3 will be randomized in a 1:1 fashion to receive either OMS721 or D5W vehicle control during the first 12 treatment weeks. Randomization for Cohort 3 will be stratified by region: North American and the United Kingdom in one strata and Asia in another strata. Study drug administration will be blinded. Additional treatment courses after the first 12 weeks in Cohort 3 will be open-label OMS721.

Treatment assignment will be blinded to all trial personnel, Omeros and its representatives, with the following exceptions:

- Investigative site pharmacist or designee who responsible for maintaining the blind at the site and will prepare and label the infusion.
- An independent site monitor (Clinical Research Associate), who will only monitor study drug accountability.
- Omeros CMC representative who will manage drug supply
- Omeros clinical data manager overseeing the implementation of the randomization module

In a medical emergency, it may be necessary to identify a subject's assigned treatment before the study has been completed and treatments unblinded. The treatment blind should only be broken if this information is necessary to treat the subject for a medical condition. In this situation, it is important that the treatment blind be maintained for all other subjects. The Omeros Medical Monitor should be contacted immediately if the treatment blind is broken. The date and reason for breaking the blind must be discussed with the Omeros Medical Monitor and recorded in the source documents.

CONFIDENTIAL

No use, disclosure or reproduction outside of Omeros without prior written authorization

Unblinding a subject's treatment assignment by the Investigator or study site personnel under any other circumstances (except as noted above) will be considered a protocol deviation.

9.1.3. Study Drug Dose Preparation

[REDACTED]

[REDACTED]

[REDACTED]

[REDACTED]

[REDACTED]

[REDACTED]

[REDACTED]

[REDACTED]

[REDACTED]

9.1.4. Storage and Handling of Study Drug Product

[REDACTED]

[REDACTED]

[REDACTED]

[REDACTED]

[REDACTED]

[REDACTED]

9.2. Study Drug Accountability

For Cohorts 2 and 3, the investigator will designate an unblinded pharmacist and/or designee who will be responsible for study drug accountability.

In compliance with U.S. Food and Drug Administration (FDA), European Medicines Agency (EMA), and other applicable regulations, records will be maintained by the investigator and/or pharmacist designee for OMS721 study drug product delivery to the site, the inventory at the site, the use of each vial, and the return of used and unused drug product, including dates and quantities. The investigator and/or pharmacist designee will maintain the investigative site's study drug accountability documentation. The documentation should include which drug product was used [REDACTED]. After the study has been completed, a copy of the investigator/pharmacy drug accountability records will be provided to the Sponsor. The original drug accountability records will be retained by the site.

9.3. Return of Drug Product

At the end of the study, the Sponsor will inform the site as to the disposition of unused drug product. If instructed, unused supplies may be destroyed at the site according to local laws, regulations, and the institution's standard operating procedures.

10. STUDY PROCEDURES

The schedule of events is summarized in Section 19.

10.1. Study Schedule

10.1.1. Screening Visit 1 (within 28 days of the first dose)

Screening evaluations will occur on two separate occasions within 28 days prior to dosing (Day 1). Before any of the screening evaluations are performed for the specific purpose of this study, the subject must provide informed consent for this study in compliance with regulations and governing IRB/IEC requirements. A subject is considered enrolled into the study once they have provided informed consent and have been assigned a subject number.

The subjects who have begun or completed Screening in Cohort 2 but have not received the first dose must sign an informed consent form and transfer into Cohort 3 prior to randomization. The

duration of the screening period for these subjects is up to 90 days. No screening procedures need to be repeated except a single 24-hour urine protein to be provided within 7 days prior to the first dose of study drug if the subject's screening 24-hour urine protein was provided more than 21 days prior to the first dose of study drug.

During Screening Visit 1, the procedures listed below will be performed and documented to determine subject eligibility prior to treatment assignment.

1. A medical history and demographic information including obtaining a history of whether a patient is anti-PLA-2R antibody positive for subjects with a history of MN.
2. Use of prior and concomitant medications, including corticosteroid dose (if applicable).
3. Vital signs including BP, pulse rate, respiratory rate (RR) and temperature (after at least 5 minutes of rest).
4. A physical examination, including height and weight. Examination of breast, rectal, and genitourinary systems may be deferred unless clinically necessary.
5. A 12-lead ECG (after at least 5 minutes of rest in the supine position).
6. Clinical laboratory tests for hematology, chemistry, coagulation, cystatin C, urinalysis, urine for inflammatory biomarkers, and anti-PLA-2R antibody in subjects with MN. See Section 12.1.1 for complete list required laboratory assessments.
7. Serum pregnancy testing in women of childbearing potential.
8. Serology tests for HIV, hepatitis B, and hepatitis C.
9. The subject will be instructed to collect urine samples for albumin/creatinine and protein/creatinine ratios on any 3 consecutive days prior to their next screening visit (i.e., a total of two three-consecutive-day collections during screening). Dispense appropriate supplies for the urine collection. NOTE: all samples for urine albumin/creatinine and protein/creatinine ratios must be collected at first void in the morning and kept in the refrigerator until the subject returns them.
10. The subject will be instructed to collect urine for 24-hour urine protein excretion and appropriate supplies will be provided. The subject will be instructed to perform the urine collection and return to the clinical site at Screening Visit 2. Subjects must return the urine to the site within 3 days of collection to prevent degradation of the sample.

10.1.2. Screening Visit 2 (At least 7 days after Screening Visit 1 and approximately 7 days prior to Treatment Visit 1)

At Screening Visit 2 the following will be performed and documented:

1. Collect urine samples from Screening Visit 1.
2. The subject will be instructed to collect additional urine samples for albumin/creatinine and protein/creatinine ratios on 3 consecutive days prior to Treatment Visit 1. Dispense appropriate supplies for the urine collection. NOTE: all samples for urine albumin/creatinine and protein/creatinine ratios must be collected at first void in the morning and kept in the refrigerator until the subject returns them.

CONFIDENTIAL

No use, disclosure or reproduction outside of Omeros without prior written authorization

3. Vital signs including BP, pulse rate, RR and temperature (after at least 5 minutes of rest).
4. Review of AEs and concomitant medications.
5. Confirmation of eGFR using the MDRD formula to assess eligibility.
6. Review of inclusion and exclusion criteria for study eligibility.

Note: Site must obtain and process urine samples prior to Treatment Visit 1.

10.1.3. Treatment Visit 1 (Day 1, approximately 7 days after Screening Visit 2)

This visit is to confirm eligibility, randomize (Cohort 2 and Cohort 3) subjects, and administer the first dose of study drug. Randomization may occur up to 2 days prior to Treatment Visit 1 if necessary for site logistical reasons provided eligibility has been confirmed. Eligible subjects for Cohort 1 will initiate treatment with OMS721. Eligible subjects for Cohort 2 and Cohort 3 will be randomized by the pharmacist or unblinded drug-designee at the study center. A computer-generated randomization will be created allocating Cohort 2 and Cohort 3 subjects to either OMS721 or vehicle.

Prior to administering the dose of study drug, the following procedures will be performed:

1. Review of AEs and concomitant medications, including corticosteroid dose (if applicable).
2. Vital signs including BP, pulse rate, RR, and temperature (after at least 5 minutes of rest).
3. ECG taken (after at least 5 minutes of rest in the supine position).
4. Laboratory samples will be collected for:
 - Hematology, chemistry, coagulation, cystatin C
 - Urinalysis
 - Serum or urine pregnancy test in women of childbearing potential. If the test result is positive then the subject will be excluded from the study
 - Blood samples for future research
 - Serum PK sample
 - Serum PD sample
 - Serum ADA sample
5. For three days prior to Treatment Visit 1, three once daily first void urine samples for albumin/creatinine and protein/creatinine ratios will be collected and brought for analysis at this visit.

Study drug will be administered by IV infusion over 30 minutes.

After dosing with study drug, the following procedures will be performed:

1. Vital signs including BP, pulse rate, RR, and temperature (after at least 5 minutes of rest) at the following timepoints: 30 minutes, 1 hour.

CONFIDENTIAL

No use, disclosure or reproduction outside of Omeros without prior written authorization

2. ECG taken (after at least 5 minutes of rest in the supine position), to be obtained immediately before the 5-minute, post dose PK sample.
3. Serum PK samples at the following timepoints after end of dosing: 5 minutes, 2 hours, and 24 hours (**Day 2**), 72 hours (**Day 4**).
4. Serum PD sample after the end of dosing: 2 hours.
5. The subject may be discharged after arrangements are made for the collection of PK samples on **Days 2 and 4**.

10.1.4. Treatment Visits 2, 3, 4 (Days 8, 15, 22; +/- 2 days)

Study drug will be administered once per week for a total of 12 weekly doses during the study. The following procedures will be performed at Treatment Visits 2, 3, and 4:

Prior to administering the dose of study drug, the following procedures will be performed:

1. Vital signs including BP, pulse rate, RR and temperature (after at least 5 minutes of rest).
2. AEs and concomitant medications, including corticosteroid dose (if applicable) will be recorded.
3. Laboratory samples will be collected for:
 - Hematology, chemistry, coagulation, cystatin C
 - Urinalysis
 - Urine for inflammatory biomarkers (visit 4 only)
 - Blood samples for future research
 - Serum PK sample
 - Serum PD sample

Study drug will be administered by IV infusion over 30 minutes.

After dosing with study drug, the following procedures will be performed:

1. Vital signs will be taken including BP, pulse rate, RR, and temperature (after at least 5 minutes of rest) at the following timepoint: 30 minutes.
2. Serum PK samples will be taken at the following timepoint: 30 minutes (visit 2 and visit 3 only).
3. Serum PD samples will be taken at the following timepoint: 30 minutes (visit 2 and visit 3 only).
4. At Treatment Visit 4, provide subjects with supplies to collect first void urine samples for urine albumin/creatinine and protein/creatinine ratios on three mornings prior to Treatment Visit 5.

10.1.5. Treatment Visit 5 (Day 29; +/- 2 days)

The following procedures will be completed at Treatment Visit 5:

Prior to administering the dose of study drug, the following procedures will be performed:

1. Vital signs including BP, pulse rate, RR and temperature (after at least 5 minutes of rest).
2. AEs and concomitant medications, including corticosteroid dose (if applicable) will be recorded.
3. For three days prior to Treatment Visit 5, three once daily first void urine samples for albumin/creatinine and protein/creatinine ratios will be collected and brought for analysis at this visit.
4. Laboratory samples will be collected for:
 - Serum or urine pregnancy test in women of childbearing potential. If the test result is positive then the subject will be discontinued from study drug administration and followed for outcome of the pregnancy.
 - Serum PK sample
 - Serum PD sample
 - Serum ADA sample

Study drug will be administered by IV infusion over 30 minutes.

After dosing with study drug, the following procedures will be performed:

1. Vital signs will be taken including BP, pulse rate, RR, and temperature (after at least 5 minutes of rest) at the following timepoint: 30 minutes.
2. Serum PK samples will be taken at the following timepoint: 30 minutes.
3. Serum PD samples will be taken at the following timepoint: 30 minutes.
4. At Treatment Visit 5, Cohort 1 subjects with stable or improving renal function should begin corticosteroid tapering and continue through the ensuing 4-week period to prednisone ≤ 6 mg (or equivalent dose), at the discretion of the Investigator.

10.1.6. Treatment Visits 6, 7, 8 (Days 36, 43, 50; +/- 2 days)

The following procedures will be performed at Treatment Visits 6, 7, and 8.

Prior to dosing with study drug, the following procedures will be performed:

1. Vital signs including BP, pulse rate, RR and temperature (after at least 5 minutes of rest).
2. AEs and concomitant medications, including corticosteroid dose (if applicable) will be recorded.
3. Laboratory samples will be collected for:
 - Hematology, chemistry, coagulation, cystatin C (visit 8 only)
 - Urinalysis (visit 8 only)

CONFIDENTIAL

No use, disclosure or reproduction outside of Omeros without prior written authorization

- Blood samples for future research (visit 8 only)
- Serum PK sample
- Serum PD sample

Study drug will be administered by IV infusion over 30 minutes.

After dosing with study drug, the following procedures will be performed:

1. Vital signs will be taken including BP, pulse rate, RR, and temperature (after at least 5 minutes of rest) at the following timepoint: 30 minutes.
2. At Treatment Visit 8, provide subjects with supplies to collect first void urine samples for urine albumin/creatinine and protein/creatinine ratios on three mornings prior to Treatment Visit 9.
3. In Cohort 1 subjects assess renal function and taper corticosteroid dose accordingly.

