For all subjects in Cohort 1 and Cohort 2, the study will consist of screening (4 weeks), treatment (12 weeks), and follow-up (6 weeks) periods.

For subjects in Cohort 3, the study will consist of screening (4 weeks), initial treatment (12 weeks) and initial follow-up (6 weeks). Cohort 3 subjects who have 24-hour urine protein $\geq 50\%$ of baseline or $> 1000\text{ mg}/24\text{ hours}$ at the end of the initial follow-up period (6-week follow-up visit) may elect to receive open-label OMS721 370 mg IV once weekly for 12 additional weeks. Follow-up for all Cohort 3 subjects will be 104 weeks from the first dose of study drug.

Subjects will have two screening visits within a 28-day screening period. Within the screening period and before the first study drug dose, consented subjects will provide three urine samples

CONFIDENTIAL

No use, disclosure or reproduction outside of Omeros without prior written authorization

(collected once daily) on each of two three-consecutive-day periods to establish baseline values of the albumin/creatinine ratio and protein/creatinine ratio. In addition, the subjects will provide one 24-hour urine protein sample to establish baseline values and confirm eligibility.

During the initial 4 weeks of treatment, Cohort 1 subjects will be maintained on their stable pre-study dose of corticosteroids. This initial 4-week treatment period will allow assessment of whether OMS721 can improve measures of renal function when administered to subjects with steroid-dependent disease when co-administered with corticosteroids. Investigators will be instructed to maintain subjects' dose of corticosteroids during the initial 4-week period unless an increase in corticosteroid dose is medically indicated.

At the end of the initial 4-week treatment period, Cohort 1 subjects will undergo corticosteroid taper over 4 weeks. The target will be a taper to ≤ 6 mg prednisone (or equivalent dose) daily. The taper schedule will be at the discretion of the Investigator. Over this period, the taper will be discontinued in subjects who have deterioration of renal function, as determined by the Investigator. Subjects will be treated with OMS721 through the corticosteroid taper and complete 12 weeks of treatment. The taper of steroids and OMS721 treatment will permit assessment of whether OMS721 allows a decrease in the dose of corticosteroid required to maintain stable renal function.

[figure not shown]

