19. APPENDICES

19.1. MDRD Equation

MDRD Equation when calculating creatinine clearance if the lab uses an Isotope-Dilution Mass Spectrometry (IDMS) method for serum creatinine determination:

$$\text{eGFR (mL/min/1.73 m}^2\text{)} = 175 \times (\text{SCr})^{-1.154} \times (\text{Age})^{-0.203} \times (0.742 \text{ if female}) \times (1.212 \text{ if African American})$$

Note: SCr = Serum Creatinine measurement should be mg/dL.

19.2. Study Schedule of Events – Cohorts 1, 2, and 3 First 12 Week Treatment Period

Period	Screening		Treatment (12 Weeks)											Follow-Up (6 Weeks)		Cohort 3 Extended Follow Up
Visit	SCR 1	SCR 2	T1			T2, T3	T4	T5	T6, T7	T8	T9	T10, T11	T12	FU 1	FU 2	FU 3-FU 9
Day	-28	-14	1	2	4	8,15	22	29	36, 43	50	57	64,71	78	85	120	176, 267, 358, 449, 540, 631, 722
		(+/- 7)				(+/ - 2)								(+/- 3)		(+/- 14)
Week	-4	-1	1			2-3	4	5	6-7	8	9	10-11	12	13	18	26,39,52,65,78, 91,104
Informed Consent, Medical History, & Physical Examination	X															
Review of Inclusion/Exclusion Criteria	X	X	X													
Randomization (where applicable)			X													
Assessment of renal function and tapering of corticosteroid dose (where applicable)								X	X	X						
Vital Signs	X	X												X	X	
Vital Signs pre-dose			X			X	X	X	X	X	X	X	X			
Vital Signs post dose: 30 min			X			X	X	X	X	X	X	X	X			
Vital Signs post dose: 1 hr			X													
ECG	X															
ECG pre-dose			X										X			
ECG post dose			X ⁷										X			
Dispense urine collection kit ¹	X	X					X			X			X	X		
Collect Urine Samples from urine collection kit ²		X	X					X			X			X	X	
Dispense supplies for 24-hour Urine protein collection ¹	X													X		X
Collect 24-hour Urine protein samples		X													X	
Urine for inflammatory biomarkers	X						X							X		X
Urinalysis ³	X		X			X	X			X				X		X
Blood Sample Collection: Chemistry, Hematology, Coagulation, Cystatin C ⁴ .	X		X			X	X			X				X	X	X

CONFIDENTIAL**No use, disclosure or reproduction outside of Omeros without prior written authorization**

Period	Screening		Treatment (12 Weeks)											Follow-Up (6 Weeks)		Cohort 3 Extended Follow Up
Visit	SCR 1	SCR 2	T1			T2, T3	T4	T5	T6, T7	T8	T9	T10, T11	T12	FU 1	FU 2	FU 3-FU 9
Day	-28	-14	1	2	4	8,15	22	29	36, 43	50	57	64,71	78	85	120	176, 267, 358, 449, 540, 631, 722
		(+/- 7)				(+/ - 2)								(+/- 3)		(+/- 14)
Week	-4	-1	1			2-3	4	5	6-7	8	9	10-11	12	13	18	26,39,52,65,78, 91,104
Anti- PLA2R ⁵	X															
Calculation of eGFR using the MDRD formula		X														

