12.9. Analysis of Other Efficacy Endpoints

Change in corticosteroid dose, based on milligrams of prednisone (or equivalent), from baseline to each scheduled visit will be summarized for each disease group for Cohort 1.

Change in serum creatinine from baseline to each scheduled visit will be summarized for each disease group, cohort and treatment. Nine-five percent CIs for the mean change from baseline will also be provided using t-distribution.

Duration of therapeutic response will be summarized descriptively by disease, cohort and treatment.

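### The planned Cohort 1 steroid summary does not estimate its stated endpoint, because recorded dose is never linked to renal stability; two protocol inconsistencies about the taper add to this.

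*Protocol*

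**What the plan says.** **Endpoint and analysis.** Protocol Section 7.3.2 and SAP Section 6 name a conditional quantity for Cohort 1: the corticosteroid dose at which renal function stays stable. For the analysis, SAP Section 12.9 says that change in prednisone-equivalent dose "from baseline to each scheduled visit will be summarized for each disease group for Cohort 1". Protocol Section 13.2.5 plans the same. Urine ratios, eGFR and serum creatinine have their own by-visit summaries (SAP Sections 12.7 to 12.9).

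**Taper.** Entry requires at least 10 mg of prednisone or equivalent (Protocol Section 8.1). The target is 6 mg or less, over four weeks (Section 7.1). At Visit 5, "Cohort 1 subjects with stable or improving renal function should begin corticosteroid tapering" (Section 10.1.5). At Visits 6, 7 and 8: "In Cohort 1 subjects assess renal function and taper corticosteroid dose accordingly" (Section 10.1.6).

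**Laboratory schedule.** The sample list for Visits 6 to 8 reads "Hematology, chemistry, coagulation, cystatin C (visit 8 only". In the schedule table (Protocol Section 19.2), the row "Assessment of renal function and tapering of corticosteroid dose (where applicable" is marked at T5 to T8. The row "Blood Sample Collection: Chemistry, Hematology, Coagulation, Cystatin C" is marked at T4 and T8 but not at T5, T6 or T7. The SAP schedule (Section 5.1) shows the same pattern.

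**Deterioration during the taper.** Section 7.1: "the taper will be discontinued in subjects who have deterioration of renal function, as determined by the Investigator". Its next sentence has subjects treated with OMS721 through the taper and finishing 12 weeks. Section 8.3.1 lists, among the circumstances that require permanent discontinuation of study drug, that "the subject experiences deterioration of renal function during corticosteroid tapering period, as determined by the Investigator".

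**The concern.** Whether OMS721 lets subjects manage on less steroid is a secondary objective and the specific purpose of the Cohort 1 taper. A subject's dose answers that question only together with the subject's renal status at that dose. The planned summary drops the second half: someone recorded at 6 mg while deteriorating contributes exactly what someone stable at 6 mg contributes. Because the protocol itself directs stable subjects towards a lower dose, part of any fall in mean dose reflects the taper instruction.

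The two protocol inconsistencies bear on the same result. Where renal function is to steer the taper but no creatinine is scheduled, sites must judge stability on older or differing information. Where two sections describe different consequences of deterioration, sites may act differently on the same event. Since Section 8.3.1 keeps subjects who stop study drug attending their visits, doses taken on and off OMS721 would then enter the same by-visit summary without distinction.

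**Working it through.** The plan gives no sample-size, power or error-rate figure for this endpoint, so there is none to reproduce. The checks are a visit count and simple dose arithmetic.

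**1. Taper assessments against scheduled draws.** Days are from Protocol Section 19.2; visit contents are from Sections 10.1.4 to 10.1.9. Creatinine is part of the chemistry panel (Section 12.1.1).

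| Visit | Day | Renal assessment for taper | Chemistry, cystatin C | Days since previous draw | Other scheduled renal laboratory measure |
|---|---|---|---|---|---|
| T5 | 29 | yes | no | 29 - 22 = 7 | first-void urine ratios |
| T6 | 36 | yes | no | 36 - 22 = 14 | none |
| T7 | 43 | yes | no | 43 - 22 = 21 | none |
| T8 | 50 | yes | yes | 50 - 22 = 28 | urinalysis |

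Three of the four assessments have no scheduled creatinine. The next draw after Day 50 is Day 85, a gap of 85 - 50 = 35 days. A four-week taper starting on Day 29 ends about Day 57, so the first scheduled creatinine after it is on Day 85, although urine ratios are collected at T9 (Day 57).

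The SAP analysis windows do not fill the gap. For treatment visits after the second they run from 3 days before to 3 days after target, so the T5 window is Days 26 to 32. An on-schedule T4 draw falls on Days 20 to 24. The creatinine and eGFR rows at T5 to T7 will be empty for on-schedule subjects.

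**2. What the mean dose change can and cannot show.** Take 16 subjects (the planned Cohort 1 size), all entering at the 10 mg minimum. The numbers deteriorating (0, 4, 8) are assumptions for illustration.

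*All reach 6 mg; f of them deteriorate while recorded at 6 mg.* Mean change = 16 × (6 - 10) / 16 = -4.0 mg for every f. Share stable at that dose = (16 - f) / 16:
- f = 0: -4.0 mg, 100% stable
- f = 4: -4.0 mg, 75% stable
- f = 8: -4.0 mg, 50% stable

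*The taper is stopped at 10 mg in f subjects and the rest reach 6 mg.* Mean change = (16 - f) × (6 - 10) / 16:
- f = 0: -4.0 mg
- f = 4: 12 × (-4) / 16 = -3.0 mg
- f = 8: 8 × (-4) / 16 = -2.0 mg

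The summary therefore responds to tapers that are halted, but not to deterioration at a dose that stays reduced.

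**3. Sections 7.1 and 8.3.1.** Both refer to Investigator-determined deterioration during the taper. Halting the taper and halting the drug could both happen in one subject. Completing 12 weeks of OMS721 and permanently discontinuing it could not, and Section 7.1 makes no exception for subjects who deteriorate.

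**The case against.** The case for the plan is substantial, and much of it stands.

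- **The taper is conditional.** It starts only if renal function is stable or improving, follows the Investigator's discretion and stops on deterioration. Recorded dose thus carries some outcome information. A reader might infer that the analysis would show success whatever the drug does; the second calculation above shows otherwise, and the plan sets no success criterion or formal test (SAP Section 12.3).
- **Other displays exist.** Dose is recorded through Follow-Up Visit 2, so a reversed taper appears in later rows. Early study-drug stops and their reasons are summarised, and renal measures are tabulated by visit. It would go too far to say the steroid data cannot be read. What is missing is the link within a subject.
- **Renal information is not wholly absent.** T5 has urine ratios and a creatinine seven days old, T9 has urine ratios, and Section 10.1.16 allows unscheduled safety assessments. The sharpest gap is T6 and T7.
- **Day 29 is not a named readout.** A reader might infer that the four-week on-steroid assessment lacks an eGFR. The documents describe an initial four-week period without fixing that day, and the schedule labels T4 (Day 22, with chemistry) as Week 4.
- **Section 7.1 may be a general plan to which Section 8.3.1 adds exceptions.** That reading is possible, but neither section says so.

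That the study is exploratory and unpowered means no error rate is affected. It does not excuse a descriptive summary from describing the endpoint it is assigned to.

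**Conclusion.** The point holds in this form: the SAP's Cohort 1 steroid summary estimates change in recorded dose, not the dose compatible with stable renal function. In the illustration the same -4.0 mg mean covers anything from 100% to 50% of subjects stable at the reduced dose. That rests on assumed deterioration counts, entry at the 10 mg minimum and a recorded dose that stays at 6 mg. Neither document defines stability or deterioration numerically, so the true size cannot be derived.

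Two inconsistencies are established from the text. Renal assessment is required at four taper visits, of which three have no scheduled chemistry or cystatin C and two (T6, T7) have no scheduled renal laboratory measure at all. Sections 7.1 and 8.3.1 describe consequences of deterioration that cannot both be followed as written. No position is taken on which clinical action is right. This should be corrected, but it does not affect the primary safety objective.

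**What to change.** **SAP Section 12.9.** Keep the dose summary and add a subject-level report of dose jointly with renal status:

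- Count a stopped or reversed taper, or a study-drug stop for deterioration, as not steroid-spared.
- Give the number of subjects at or below the protocol's own 6 mg target without Investigator-determined deterioration, with an exact confidence interval, and pre-specify the visit at which this is scored.
- Show eGFR and creatinine change at the nearest scheduled draw beside it.
- State that, with no control arm in Cohort 1, the result is descriptive and cannot by itself attribute steroid reduction to OMS721.

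**Protocol.** The sponsor should reconcile the renal-assessment instruction with the laboratory schedule at T5 to T7, and Section 7.1 with Section 8.3.1.

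**Cost.** The SAP change is a small amount of analysis on doses, laboratory values and study-drug stop reasons already collected. It should be confirmed that the case report form also captures deterioration when the taper stops but the drug does not, because the protocol text requires a recorded reason only for stopping study drug or withdrawing. The protocol changes need a clarification, or an amendment with ethics approval (Section 16.1) if the laboratory schedule itself changes. Cohort 1 is already under way, so a schedule change would not reach subjects who have passed those visits.
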